### 13.1.2 DOSAGE AND ADMINISTRATION

Both products will be used and dosed according to the USPI and SOC.

The dose administered will be based on the subject's BW and age, and adjusted based on clinical response and laboratory parameters according to SOC and PI's judgement.

These procedures are informed by the main treatment guidelines, as well as in the USPI of Tirosint®-SOL and LT4 tablets ([Synthroid USPI](#), [Tirosint®-SOL USPI](#)), as described in **Section 11.3**.

**Further to these general principles, Investigators are required to follow the SOC in order to define the correct dose and treatment goal for each subject.**

Initial Dosing in newly diagnosed neonates:

- Replacement therapy with LT4 should be started as promptly as possible upon diagnosis of CH.
- **Inclusion in the study must not delay the start of LT4 treatment.**
- Initial neonate LT4 dose should be between 10-15 mcg/kg;
- The initial dose should take into account the severity of the disease; and
- The goal of therapy should be to normalize FT4 into the upper half of the reference range and TSH within the reference range (it is suggested, within the mid- to lower half of the reference range whenever appropriate).

Initial Dosing in infants already under LT4 therapy:

- Subjects will be switched directly from crushed LT4 tablets to Tirosint®-Sol or continue on crushed LT4 tablets, with **no treatment interruption**.
- Same dose used before screening should be maintained, if replacement is adequate at screening/inclusion; or
- Dose should be adjusted at inclusion, if needed based on laboratory parameters and clinical response.

Dosing throughout study in neonates and infants:

- Dose adjustments can be done whenever required throughout the study and will be defined based on the evaluation of T4 and TSH values and clinical response according to SOC; and
- Therapy should aim to maintain serum TSH concentration in the age specific laboratory reference range (it is suggested, to target the mid- to lower half of the reference range whenever appropriate) and serum T4 concentration in the upper half of the age specific laboratory reference range.

If dose fine tuning is required, which cannot be obtained with the available strengths, alternating two strengths over the course of the week may be allowed. All dosing schemes must be documented in the EDC.

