All eCRF users will receive a User Manual and training on system use prior to enrollment of the first participant. Access to the eCRF will be controlled by the Sponsor (or designee) through provision of user-specific login credentials that will only be provided after documentation of eCRF training. All personnel authorized to make entries in the eCRF will be listed by name, title, signature, and initials. The list should be updated during the study duration, if needed.

The PI and/or designated clinical site personnel should immediately alert the clinical monitor and/or Sponsor designee about eCRF operational issues. In the unlikely event that the eCRF is unavailable for an extended period of time, the clinical monitor may direct designated clinical site personnel to utilize paper CRFs for data collection.

All data originators (i.e., PI, designee(s) and participants) at each clinical site will be documented and made available, if needed. Each data element in the eCRF will have an associated identifier

comprised of a data originator, date/time stamp, and clinical trial participant, and both the data element and identifier will be present in a human-readable audit trail.

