3 STUDY DESIGN

This is a multi-center, prospective, parallel-group, open-label, randomized clinical study in one hundred and twenty-six (126) subjects (neonates and infants diagnosed with congenital hypothyroidism (CH)).

Subjects will be randomized in a 2:1 ratio to Treatment (Tirosint®-SOL) or Control (levothyroxine sodium crushed tablets).

Newly diagnosed neonates will be randomly assigned to start therapy with Levothyroxine (LT4) at the initial dose recommended by the Standard of Care.

Infants already on LT4 therapy will continue at the same daily dose within the randomly assigned treatment group (dose adjustments are allowed, if needed based on laboratory parameters and clinical response).

Once enrolled, subjects will be treated and followed for 12 months (± 1.5 months), participating in 7-8 study visits, consisting of 6-7 in-clinic and 1-2 (or more if follow-up

visits are required) telemedicine visits. The total number of visits depends on the age at inclusion as reported in the Tables 1 Schedule of Evaluations and Table 2 Outline of Visit Schedule based on Age of the study protocol.

In-clinic visits are performed between 3-4 weeks after randomization, when the subject is 4, 6, and 9 months of age, and then every 3 months as required depending on the age at the inclusion. Telemedicine visits will be performed between 1-2 weeks after randomization, when the subject is 2 months of age, if applicable, and any time an additional follow-up is required for TSH and thyroxine (T4) monitoring.

For further details refer to Study Protocol n. 20US-T414 final version v2.0, Release date: September 7, 2023.

The study was originally planned to enroll a total number of 126 subjects (84 Treatment and 42 Control), expected between September 2021 and July 2022. Despite the extension of the study timeline, a protocol amendment and the efforts by the sites, the enrollment (screening) was closed on 31 March 2024 with a total of 31 randomized subjects, since reaching the enrollment target appeared no longer practicable within reasonable timeframe.

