3.4 CHANGES FROM STUDY PROTOCOL

Section 19.2 Population for analysis:

The following subject populations were foreseen:

- Full Analysis Set (FAS): all randomized subjects;
- Per Protocol Set (PPS): all randomized subjects with no major protocol deviations; and
- Safety Analysis Set (SAF): all randomized subjects who received at least 1 dose of study medication.

Due to the premature termination of the study and the limited sample size the Per Protocol Set will not be considered for the final analysis.

Section 19.3.1 General Statistical Methods:

Due to the fast changing measurements in the specific population, in relation to growth, the last observation carried forward (LOCF) method will not be used to deal with missing data or in the case of early study discontinuation and missing data will not be replaced.

Section 19.3.2 Efficacy outcomes:

Due to the premature termination of the study and limited sample size all the efficacy analyses will be considered exploratory. LT4 dose/kg, laboratory parameters (TSH and FT4), “Parents’ Satisfaction Questionnaire” will be analyzed with a mixed model adjusted with Kenward-Roger method and considering as first choice the unstructured covariate matrix (other matrixes will be considered if there will be convergence problems). Variables newly diagnosed neonates vs infants already on LT4 therapy and center will not be considered in the models. Normal distribution for LT4 dose/kg, laboratory parameters (TSH and FT4), “Parents’ Satisfaction Questionnaire” will be tested with Shapiro Wilks, if data result not distributed as a normal distribution a log transformation will be applied. LT4 dose/kg, TSH and FT4 levels and Parents’ Satisfaction Questionnaire score at each visit will be compared between treatment groups by Wilcoxon Mann-Whitney test.

Section 19.3.3 Exploratory outcomes:

Time to TSH and FT4 normalization in the neonates will not be evaluated between the treatment groups due to the low number of neonates enrolled (3 randomized to Tirosint-SOL and only 1 to Control).

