6.1.2 Secondary efficacy variables

Laboratory parameters

- Thyroid Stimulating Hormone (TSH);
- Free Thyroxine (FT4);
- Number of events of TSH values above 4.5 mU/L;
- Number of events of FT4 values below the middle of the laboratory normal range

Frequency of dose adjustments

Percent number of subjects (%) who need a dose adjustment in the long-term follow up phase.

Parents' satisfaction questionnaire (PSQ)

The Parents' Satisfaction Questionnaire is completed by the parents/guardian in the eDiary:

at V1 only for infants who are already on TH therapy, and 0-3 days before in-clinic visits for all subjects.

Parents answer questions about the following topics:

- Coping and mental well-being;
- Drug preparation & administration;
- Treatment satisfaction; and
- Medication preference.

The PSQ score at each visit will be computed as sum of all questions scores assigned as reported in Appendix 3.

Caregiver administered Children's Acceptance Tool (CareCAT)

This questionnaire is completed within the eDiary during the first, the third and the eighth week of treatment.

Descriptors:

Swallows well – Medicine is swallowed down

- Observing the act of swallowing the medicine – '[I see that she] drinks the medicine and swallows'
- Ingesting the medicine in absence of negative behaviors – 'He swallows and does not give me a hard time'

Refusal – Resistance of the child (e.g. fighting, crying)

- Defensive behavior preventing the intake of medicine – 'By pushing the spoon' or 'fights with her hands' or 'turns away her head'
- Spitting up – Some medicine is coming out of the mouth immediately
- Forcing the medicine out actively – 'He spits or maybe blows the medicine out'
- Medicine passively leaving the mouth ('overflow' or 'spilling') – 'When the medicines runs down the mouth'

Vomiting – Within 30 minutes after swallowing the medicine the child brings up something [vomits]

- 'She takes out the medicine after feeling nauseous, then vomits it with food'

Medication not taken – No medicine went into the mouth of the child

- No oral intake of medicine – 'She does not want [to take the medicine] until the medicine did not get in [the mouth]'
- Intake without ingesting – 'I have tried to give her but [the medicine] was still not swallowed'

Growth assessments

The following variables about growth are collected: length (cm), weight (Kg) and head circumference (cm).

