9.4.2 Secondary efficacy analyses

Laboratory parameters (TSH and FT4)

Laboratory parameters (TSH and FT4) will be analysed at each time point by means of analysis of covariance (mixed model), including basal value, treatment group, age at randomization and interactions between visit and treatment group as covariate.

Normal distribution for TSH and FT4 will be tested with Shapiro Wilks, if data result not to be distributed as a normal distribution a log transformation will be applied.

The mixed model will be adjusted with Kenward-Roger method and the unconstructed covariance matrix will be used as first choice (other matrixes will be considered if there will be convergence problems).

Summary descriptive statistics will be provided for each laboratory parameter. TSH and FT4 levels at each visit will also be compared between treatment groups by Wilcoxon Mann-Whitney test. This analysis will also be repeated stratified on neonates and infants.

Laboratory data will also be listed with clinically significant information.

TSH values above 4.5 mU/L

The events of TSH values above 4.5 mU/L will be compared between treatment groups at each visit and aggregate from Visit 2 to the last available visit using a Chi-squared test or, when the expected values in any of the cells of a contingency table are below 5 or the total number of observations is less than 20, Fisher exact test as appropriate.

FT4 values below the middle of the laboratory normal range

The events of FT4 values below the middle of the laboratory normal range will be compared between treatment groups at each visit and aggregate from Visit 2 to the last available visit using a Chi-squared test or, when the expected values in any of the cells of a contingency table are below 5 or the total number of observations is less than 20, Fisher exact test as appropriate.

Parent satisfaction assessed by “Parents’ Satisfaction Questionnaire”

Parent satisfaction assessed by “Parents’ Satisfaction Questionnaire” score at V3, V5, V6, V7, V8, V9, V10, V11 will be analyzed by means of analysis of covariance (mixed model), including treatment age at randomization and interactions between visit and treatment group as covariate.

Normal distribution for Parents’ Satisfaction Questionnaire score will be tested with Shapiro Wilks, if data results not be distributed as a normal distribution a log transformation will be applied.

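### The satisfaction model leaves out the Visit 1 score that parents of 27 of the 31 children were asked to give, so chance differences at entry carry into the estimate and some precision may be lost

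*SAP*

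**What the plan says.** SAP 6.1.2 has the questionnaire completed "at V1 only for infants who are already on TH therapy, and 0-3 days before in-clinic visits for all subjects". The infants' earlier treatment is given in protocol 13.1.2: "Subjects will be switched directly from crushed LT4 tablets to Tirosint®-Sol or continue on crushed LT4 tablets". For infants, V1 is therefore an entry measure on the same instrument, about the comparator formulation.

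For the satisfaction outcome, SAP 9.4.2 states: "score at V3, V5, V6, V7, V8, V9, V10, V11 will be analyzed by means of analysis of covariance (mixed model". V1 is not among those visits. The terms of the model are treatment, age at randomization and visit-by-treatment (a comma seems to have dropped out between the first two), so no entry score is among them. For TSH and FT4 the same section specifies a model "including basal value, treatment group, age at randomization and interactions between visit and treatment group as covariate".

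The only other place where V1 could appear is the by-visit descriptive statistics and Wilcoxon tests in SAP 9.4.2, which adjust for nothing. The baseline table in SAP 9.3 does not list the questionnaire. Protocol 19.3.2 named V1 among the satisfaction visits to be analysed for infants already on therapy. The SAP version history says that the visits are now specified, but neither it nor SAP 3.4 gives a reason for leaving V1 out.

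**The concern.** Parent satisfaction and ease of administration form one of the four main objectives (protocol 10.1, SAP 3.1), although SAP 6.1.2 classes the questionnaire as a secondary efficacy variable. SAP section 3 reports "a total of 31 randomized subjects". At 2:1 that is about 10 Control families.

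The score sums all questions, and one of the four topics is coping and mental well-being, which plausibly varies between families whatever the formulation. In a trial this small the arms can differ noticeably at entry by chance. If the score is correlated over time, part of that difference reappears at later visits inside the estimated formulation effect. An entry measurement that could absorb it is already being collected.

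**Working it through.** **Plan's own figure.** The documents size only the LT4 dose comparison. With a difference of 1.2 (20% of 6), SD 2 and two-sided 0.05, the t-test at 68 + 34 has 80.8% power, so the stated 102 reproduces. Nothing is sized for the questionnaire, so the check below stands alone.

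**Who was due to give a V1 score.** SAP 3.4 gives the neonates as "3 randomized to Tirosint-SOL and only 1 to Control". So 31 − (3 + 1) = 27 infants, and 27/31 = 87%. This is the number asked; the number who answered is not stated.

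**Assumptions.** The infants split 18:9 (2:1; the actual split is not given). Results are in SD units of the score (its SD is not given). r is the correlation of V1 with a later score (not given, so a range is shown). All 27 V1 forms are present.

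**Size of a chance entry difference.** SD = √(1/18 + 1/9) = 0.41. The chance that it exceeds 0.5 in either direction is P(|Z| > 0.5/0.408) ≈ 22%. For splits from 17:10 to 19:8 the SD is 0.40 to 0.42.

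**Simple expectation.** Among infants, a chance entry difference d carries over as r × d: 0.12, 0.20 and 0.29 SD at r = 0.3, 0.5 and 0.7 for d = 0.408. Adjustment multiplies the residual variance by 1 − r², so the standard error falls by 4.6%, 13% and 29%, before paying for extra parameters.

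**Simulation that pays for them.** This used one visit, no true effect, 18:9 infants plus 3:1 neonates, and 8,000 runs per r. The planned-type model is treatment + age. The adjusted model adds the infant-centred V1 score (0 for neonates) and a neonate/infant indicator.

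| r | 95% CI width, planned | 95% CI width, adjusted | ratio | estimate when infants differ by about +0.41 SD at V1: planned | adjusted |
|---|---|---|---|---|---|
| 0 | 1.580 | 1.628 | 1.03 | −0.01 | −0.02 |
| 0.2 | 1.580 | 1.596 | 1.01 | 0.07 | 0.00 |
| 0.3 | 1.578 | 1.559 | 0.99 | 0.12 | 0.01 |
| 0.5 | 1.582 | 1.434 | 0.91 | 0.19 | 0.01 |
| 0.7 | 1.580 | 1.221 | 0.77 | 0.27 | 0.01 |

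Averaged over all runs, the estimate lay between −0.002 and 0.004 under both models. The shift in the fifth column is therefore conditional on the imbalance that happens to occur; it is not a bias of the method.

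**The case against.** The strongest objection concerns the V1 score itself. The procedure list in protocol 16.1 places randomisation, dispensing and administration training before the request to complete the questionnaire, and the trial is open-label. If knowing the allocation colours V1 answers, adjustment treats that as chance imbalance and removes it. A 0.41 SD shift of that kind (assumed size) would move the adjusted estimate by about 0.19 SD at r = 0.5, an error that the planned model does not have. This stands. It is why the adjusted model should be added to the planned one and checked on V1 forms completed before allocation.

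Completeness is also open. SAP 10.1.4 reports poor adherence to the daily diary, and under SAP section 8 missing values are not replaced, so a plain covariate would drop infants with no V1 form. Protocol 15.1.2 asks sites to have missing questionnaires completed on site, which helps by an unknown amount. This also stands and shapes the fix.

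The TSH/FT4 comparison is imperfect. Neonates have diagnostic hormone results recorded at V1 but no V1 questionnaire by design, and the LT4 dose/kg model has no baseline term either. SAP 3.4 also removed the neonate/infant term from the models, and the fix brings back something close to it. These points explain why a baseline term could not simply be copied across. They are not a reason to leave a collected entry score unused.

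All efficacy analyses are exploratory (SAP 9.4), which lowers the stakes. Estimates and intervals will nevertheless be the main product of a 31-child trial.

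**Conclusion.** The point holds as a missed adjustment. The planned model ignores an entry score due from 27 of 31 families. A typical chance imbalance (0.41 SD) would shift the realised estimate by about 0.12, 0.19 or 0.27 SD at r = 0.3, 0.5 or 0.7. Adjustment would narrow the 95% CI by about 1%, 9% or 23%. At or below about r = 0.2 there is no gain, and the interval is at most 3% wider. All of this rests on the assumed r, the assumed 18:9 split and complete V1 forms.

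Three stronger readings are tempting, and the documents do not support them:

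- **That the planned analysis is biased.** Under randomisation, entry differences are chance, and the unadjusted interval already allows for them in its width.
- **That family differences dominate the contrast.** The item scoring (SAP Appendix 3) is not visible in the text available. Three of the four topics plausibly follow the product, and r may be low in the arm that changes formulation straight after V1.
- **That the gain is larger.** With an assumed 21:10 split, the formula t(0.975, 27) × s × √(1/21 + 1/10), where s² = (27/31)(1 − r²) + 4/31, takes the half-width from 0.79 to 0.76, 0.70 and 0.60 at r = 0.3, 0.5 and 0.7. It uses the same degrees of freedom for both models and so charges nothing for the two added terms.

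**What to change.** Keep the planned model and add one V1-adjusted model to SAP 9.4.2. Pre-specify it if results are not yet known; otherwise label it clearly as supplementary.

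1. Add the V1 score, centred on the infants' mean and set to 0 where there is none, with an indicator for no V1 score. Neonates and infants with a missing V1 form then stay in.
2. Name the V1 score explicitly as the entry value. SAP 4.1 defines baseline as before the treatment start date, while protocol 16.1 prefers treatment to start on the day of randomisation, so same-day forms could be lost.
3. Report how many V1 forms were completed, and how many before allocation. Protocol 18.1 says that each eCRF data element has an identifier "comprised of a data originator, date/time stamp, and clinical trial participant"; this must be set against the randomisation time, which has to come from the randomisation system.
4. Repeat the adjusted model using only V1 scores completed before allocation. If few exist, treat the adjusted result as supportive only.
5. Show V1 as a baseline row and leave it out of the by-visit Wilcoxon tests, so that a pre-treatment p-value is not read as a formulation effect.

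The cost is a short SAP addition, one extra table and two degrees of freedom, with no new data collection. The remaining risk is V1 answers coloured by known allocation, which step 4 addresses only as far as pre-allocation forms exist.

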d The procedures conducted at each visit may take place on multiple days (0-7 days) all within the allowed time frame.

e Including standard health maintenance exam for age and vital signs (Heart Rate and Temperature).

f Including length, body weight (BW) and head circumference.

Visit	V1	Treatment start	V2	V3	FU1 a	V4	V5	V6	V7	V8	V9	V10	V11	FU2 b
Age at Visit	Varies		Varies	Varies		2 months (60 days ±7)	4 months (120 days ±14)	6 months (180 days ±14)	9 months (270 days ±14)	12 months (365 days ±21)	15 months (455 days ±21)	18 months (545 days ±21)	21 months (635 days ±21)	
Blood Sampling for TFTs g	X h		X m	X	X	X	X	X	X	X	X	X	X	X
Dosing Evaluation	X		X	X	X	X	X	X	X	X	X	X	X	X
eDiary dispensing and instruction	X													
Treatment														
Daily eDiary														
CareCAT i			X	X		X	X	X	X	X				
Parents' Satisfaction Questionnaire j	X			X			X	X	X	X	X	X	X	
Subject Visit Reminder Card	X			X			X	X	X	X	X	X		
Drug dispensing and instruction k	X			X			X	X	X	X	X	X		
Drug return				X			X	X	X	X	X	X	X	
Treatment compliance			X	X	X	X	X	X	X	X	X	X	X	X
End of Study l										X	X	X	X	

g May be collected at the study visit or prior (0-7 days) to the study visit, within the visit allowed time frame.

b Subject's own lab results are acceptable. For newly diagnosed neonates, the lab results obtained from routine diagnostic workup will be recorded at V1; labs do not need to be repeated at Screening Visit for the purpose of the study. For infants who are already on TH therapy, the lab results obtained during routine follow-up will be recorded at V1, if not older than 4 weeks (<28 days); blood will be collected and analyzed if a lab report dated less than 28 days is not available, or if necessary as per Investigator's medical judgement.

i CareCAT will be completed after the daily drug administration in the eDiary during the first week of treatment (on days 1-7), during the third week of treatment (on days 15-21), and during the eighth week of treatment (on days 50-56).

j Parents' Satisfaction Questionnaire will be completed in the eDiary at V1 only for infants who are already on TH therapy and 0-3 days prior to all other in-clinic visits for all subjects.

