### **15.1.3 CAREGIVER ADMINISTERED CHILDREN'S ACCEPTANCE TOOL (CareCAT)**

CareCAT is a 5-point nominal scale used to assess the acceptance of oral medicines in infants and toddlers who are unable to verbally give their opinion about a medicine ([Blume 2018](#)).

The CareCAT is designed to be administered by parents/caregivers in their home environment. This questionnaire will be completed within the eDiary during the first, the third and the eighth week of treatment.

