3.2 SAMPLE SIZE

Subjects were randomized in a 2:1 ratio to Treatment (Tirosint®-SOL) or Control (conventional therapy with LT4 crushed tablets). Considering a mean value of 6 mcg/kg/day of LT4 dose at 12 months of age and a standard deviation of 2 mcg/kg, a sample size of 102 neonates and infants (68 Treatment and 34 Control) will have 80% power to detect a difference of 20% in the LT4 dose between the groups using an independent t-test with a 0.050 two-tailed significance level. To account for a drop-out rate of maximum 20%, 126 neonates and infants will be enrolled in the study (84 Treatment and 42 Control) (Peroni 2013).

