9 STATISTICAL METHODOLOGY

9.1 GENERAL METHODOLOGY

Descriptive statistics

Categorical variables will be summarized by frequency (n) and percentages (%) and quantitative (continuous) variables using measures of central tendency (mean, median) and dispersion (minimum & maximum; 95% confidence intervals; values defining the limits of the 2nd and 3rd quartiles (25th percentile, 75th percentile); and the standard deviation.

P-values and Type I error

All p-value(s) will be rounded to three decimal places. Statistical significance will be declared if the rounded p-value is less than 0.050.

Two-sided 95% confidence intervals (CI) will be calculated.

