The mixed model will be adjusted with Kenward-Roger method and the unconstructed covariance matrix will be used as first choice (other matrixs will be considered if there will be convergence problems).

Summary descriptive statistics will be provided for Parents’ Satisfaction Questionnaire score and the results at each visit will also be compared between treatment groups by Wilcoxon Mann-Whitney test.

Caregiver Administered Children’s Acceptance Tool (CareCAT)

The subject medicine acceptance assessed by “Caregiver Administered Children’s Acceptance Tool (CareCAT)” will be analyzed during the first week, the third week, and the eighth week

of administration and analyzed by day in each week and by week comparing the treatment groups by means Cochran-Mantel-Haenszel χ^2 test. Descriptive statistics on aggregate CareCAT results overall and by week will also be provided.

Dose re-adjustment

The number of subjects who need a dose re-adjustment during the long-term follow-up phase (Visit 4 to Visit 11) of the study will be compared between treatment groups by means of Chi-squared test or, when the expected values in any of the cells of a contingency table are below 5 or the total number of observations is less than 20, Fisher exact test as appropriate.

Growth pattern

Summary descriptive statistics on length (cm), weight (Kg) and head circumference (cm) will be provided. Results at each visit for each parameter will be compared between treatment groups by Wilcoxon Mann-Whitney test.

Growth assessment parameters will also be listed with clinically significant information.

Signs and symptoms of hypo- and hyper-thyroidism

Number of subjects experiencing hypothyroidism/hyperthyroidism signs or symptoms will be summarized by hypothyroidism, hyperthyroidism and overall.

The number of subjects experiencing at least one sign or symptom will be compared between treatment groups using a Chi-squared test or, when the expected values in any of the cells of a contingency table are below 5 or the total number of observations is less than 20, Fisher exact test as appropriate.

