10.1.4 Other tolerability parameters

Compliance

Compliance will be computed for each subject by visit considering as start date the first date of treatment after randomization reported on the LT4 treatment forms and as end date the Date of Last Study Drug Dose Taken reported in the end of study form.

The number of expected days of treatment will be computed by visit for each subject and the number of days of treatment will be computed based on the study medication diary considering the autofilled treatment day number with information about time of administration or strength not missing.

Due to the lack of adherence with the compilation of the daily diary, compliance will be calculated and reported for informative purposes only.

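### The weekly CareCAT test names no per-child unit; if daily ratings are the records, its nominal 5% level is exceeded

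*SAP*

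**What the plan says.** The footnote on CareCAT to Protocol Table 1 has the caregiver complete the tool after each daily dose "during the first week of treatment (on days 1-7), during the third week of treatment (on days 15-21), and during the eighth week of treatment" (days 50-56). That is up to seven ratings per child in each of three weeks. Protocol 15.1.3 describes the instrument: "CareCAT is a 5-point nominal scale used to assess the acceptance of oral medicines in infants and toddlers".

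SAP 9.4.2 plans that the ratings be "analyzed by day in each week and by week comparing the treatment groups by means Cochran-Mantel-Haenszel" chi-squared test, and adds descriptive summaries of aggregate results overall and by week. Protocol 19.3.2 names the same test for the three weeks. Neither document states the strata, which Cochran-Mantel-Haenszel (CMH) statistic is meant, or what one record is in the weekly test.

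Acceptance is one of the four main objectives (Protocol 10.1, SAP 3.1). SAP 6.1.2 lists CareCAT as a secondary efficacy variable, and SAP 3.4 and 9.4 declare all efficacy analyses exploratory. SAP 9.1 nevertheless keeps a threshold for every p-value: "Statistical significance will be declared if the rounded p-value is less than 0.050".

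**The concern.** The by-week test is planned in addition to the by-day tests, so it has to combine the days somehow. The SAP gives no rule for reducing a child's week to one value. Its definitions section (SAP 4) has none. SAP 6.1.2 sets out a computed score for the parents' questionnaire but only category descriptors for CareCAT. Mixed models are specified for LT4 dose, TSH, FT4 and the questionnaire, but nothing comparable for CareCAT. Child-days are therefore the natural input.

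The same caregiver rating the same child on consecutive days will tend to give similar answers. A CMH test on child-days counts them as separate evidence:

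- Pooled over days, all child-days are treated as independent.
- Stratified by day, the variance is added over days as if each day had a fresh sample of children.
- Stratified by child, each stratum holds one arm only and carries no information on treatment.

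At stake is the credibility of the weekly acceptance p-values. With 31 randomized children, a small p-value could reflect repeated ratings of a few of them.

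**Working it through.** **The plan's own figures.** The documents give no power or error rate for CareCAT beyond the 0.050 threshold. The only power calculation concerns LT4 dose: "Considering a mean value of 6 mcg/kg/day of LT4 dose at 12 months of age", SD 2, "using an independent t-test with a 0.050 two-tailed significance level". It reproduces: a 20% difference is 1.2; 1.2 / (2 × √(1/68 + 1/34)) = 2.86, which gives 80.8% power by the noncentral t distribution, against the stated 80%. It says nothing about CareCAT.

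**Inputs from the documents.** Up to m = 7 ratings per child-week (Protocol Table 1); nominal level 0.050 (SAP 9.1); 31 randomized at 2:1 (SAP 3), or about 21 v 10 (31 × 2/3 = 20.7).

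**Assumptions, not in the documents.** The exact 21:10 split; a yes/no outcome ('swallows well' or not, 1 df); every child rated the same number of days; and the within-child correlation (ICC), shown over a range.

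**Formula.** Design effect DE = 1 + (m − 1) × ICC. Actual level = 2 × [1 − Φ(1.96/√DE)]. For m = 7 and ICC 0.2, DE = 1 + 6 × 0.2 = 2.2 and 1.96/√2.2 = 1.32, which gives 18.6%.

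| ICC | DE (m = 7) | 7 ratings | 5 ratings | 3 ratings |
|---|---|---|---|---|
| 0 | 1.0 | 5.0% | 5.0% | 5.0% |
| 0.05 | 1.3 | 8.6% | 7.4% | 6.2% |
| 0.2 | 2.2 | 18.6% | 14.4% | 9.8% |
| 0.5 | 4.0 | 32.7% | 25.8% | 16.6% |
| 0.7 | 5.2 | 39.0% | 31.5% | 20.6% |

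**Simulation under no difference** (21 v 10 children, seven ratings, 60% or 80% 'swallows well', 1,000 to 2,000 runs per cell):

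| ICC | CMH pooled | CMH stratified by day | Per-child proportion, Wilcoxon |
|---|---|---|---|
| 0.2 | 18-19% | 18-22% | 5% |
| 0.5 | 34% | 31-33% | 4-5% |
| 0.7 | 40% | 40-41% | 4% |

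Stratifying by day does not remove the inflation. Over all settings run, the per-child Wilcoxon test rejected in 4.0-5.5%.

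**Five categories.** With a general-association statistic on all five categories, the simulated pooled rates are 32%, 65% and 77% at ICC 0.2, 0.5 and 0.7.

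**Irregular diaries.** With an average of three of seven days recorded at random and 75-85% 'swallows well', pooled simulation gives about 11%, 19-20% and 24-25% at the same ICCs. That is somewhat above the table's column for exactly three ratings, because the number of ratings then varies between children.

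**By-day tests.** Each uses one rating per child, so m = 1, DE = 1 and this problem does not arise.

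**The case against.** The strongest reply is that the SAP never says child-days are pooled. One weekly value per child, with CMH strata such as the randomization age group or site, also fits the words, and would hold the level near 5%. The SAP foresees weekly aggregation for its descriptive tables. This stands to the extent that the established defect is an undefined unit. It does not remove the point, because a nominal five-category rating cannot become one weekly value without a rule, and none is given.

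Second, any single inflation figure depends on a correlation, a dichotomy, complete diaries and a split between arms that the documents do not supply. This stands, and the figures are conditional for that reason. A reader might infer that a rate of 18-40% is a property of the plan; the documents do not support that.

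Third, a reader might take SAP 10.1.4 ("Due to the lack of adherence with the compilation of the daily diary") as proof that CareCAT records are incomplete. That sentence concerns compliance computed from the medication diary. CareCAT sits in the same eDiary, so gaps are plausible, but its completeness is not reported.

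Fourth, all efficacy analyses are exploratory. This lowers the severity, but the SAP will still label weekly results significant below 0.050.

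**Conclusion.** The concern holds in conditional form. The SAP plans a weekly CMH test on an outcome rated up to seven times per child without defining a per-child value or a method for correlated ratings. If child-days are the records, the test is anti-conservative, pooled or stratified by day. For a 1-df yes/no outcome with seven ratings and about 21 v 10 children, the level is about 9% at ICC 0.05, rising to 39% at ICC 0.7. With three ratings it is about 10-21% for ICC 0.2-0.7. With the five-category general-association statistic it is higher. The ICC, the dichotomy, the diary completeness and the split are assumptions.

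A reader might infer that the trial loses control of a confirmatory error rate. It does not: CareCAT is secondary and exploratory in the SAP, although acceptance is a main objective. The harm is misleading weekly p-values. This should be fixed, but it does not threaten the trial's validity.

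**What to change.** Make the child the unit of the weekly test in SAP 9.4.2:

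- For each child and week, compute one prespecified summary, for example the proportion of recorded days rated 'swallows well', and compare arms by a Wilcoxon test.
- Alternatives are a permutation test that reassigns whole children, or a GEE clustered on child with a small-sample correction. Without the correction, a GEE with about 10 control children rejected in roughly 6-9% of null simulations with complete ratings.
- Show the number of recorded days per child by arm and week, so that uneven completion is visible.
- If a CMH test is kept for the weekly comparison, state its record (one per child), strata and statistic.
- The by-day CMH tests may stay as planned, with strata and statistic named.

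The cost is a few lines of SAP text and minor programming. A yes/no summary loses some detail on refusal, spitting, vomiting and doses not taken, which the planned descriptive tables can still show. Weekly p-values will probably be larger than with pooled child-days.
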